2.4 Operational definitions

(1) Medication adherence: Medication adherence is defined as the level of patients in complying with the medications prescribed by healthcare providers. Such level of compliance is measured through a self-reported scale MALMAS (Chung et al. 2015) which had been validated among T2DM patients in Malaysia.

(2) T2DM Malay patients: Type 2 Diabetes Mellitus Malay patients of this study refers to all the patients who are prescribed with oral anti-hyperglycaemic agents (OHA) and obtain their medications supply from the pharmacy department of KS-HC and PJ-HC during the study period. Such T2DM patients whose identity card show their religion as Islam, will be considered as Malay T2DM patients for this study.

(3) Cluster Randomized Controlled Trial: Cluster Randomized Controlled Trial refers to the study design employed by this study with accordance to the Recommendations for Intervention Trials “SPIRIT” (Chan et al. 2013) and will be reported in accordance to the Consolidated Standards of Reporting Trials (CONSORT) Statements with extension to cluster randomized trials (Campbell et al. 2012).

(4) Structured group based intervention: The structured group based intervention of this study refers to the program “Know Your Medicine – Take it for Health” which was formulated and employed by the Pharmaceutical Services Division of Sarawak State Health Department in late 2016 under the national campaign “Know Your Medicine” to promote medication adherence among T2DM Malay patients. The official name of the intervention is “Kenali Ubat Anda –

Ambillah untuk Kesehatan” in Malay language or “Know Your Medicine – Take it for Health” in English with abbreviation KYM-TIFH.

(5) Effectiveness: The effectiveness of this study refers to the improvement of medication adherence level among T2DM Malay patients before and after the SGBI with such improvement having significant difference as compared to the results in control group. Furthermore, the effectiveness of the SGBI will be complemented by the qualitative data through focus group discussion and semi-structured interview.

(6) Complications: The complications in this study refers to the diabetes-related complications including retinopathy, nephropathy, diabetic foot problems, ischemic heart disease and stroke that had been diagnosed by doctors and were documented in patients’ medical records during the period of study.

Chapter 3: Research Methodology

Overview

This chapter depicts the research paradigm and methodology employed to achieve the three specific objectives of this study. For the first research objective, which is to measure the effectiveness of the KYM-TIFH, positivist approach with experimental study design is best suited. In specific, experimental study with randomized controlled trial (RCT) design is employed as RCT is positioned at higher level of evidence-based medicine pyramid after case studies, case-control and cohort studies (Murad et al. 2016). Nevertheless, the findings from the RCT on the effectiveness of the KYM-TIFH will be triangulated by the findings from subsequent focus group discussion (FGD) and semi-structured interview (SSI) which employ interpretivist or qualitative approach. The aim of the interpretivist approach is to obtain the experience and attitudes of respondents about the KYM-TIFH in a flexible and iterative manner (Berg and Lune 2004; Smith 2002).

For the second objective, which is to test the predictive capacity of the integrated model on medication adherence, positivist approach with cross-sectional analysis is best suited. The point of assessment will be at the end of the trial. For the third objective, which is to test the impact of KYM-TIFH on the psychosocial variables that lead to medication adherence, the positivist approach with prospective analysis to examine how the psychosocial variables change before and after the intervention and cross-sectional analysis to examine whether there is significant difference of the change in psychosocial variables between participants from intervention group and control group.

3.1 Study Design

This study aims to assess the effectiveness of a structured group based intervention specifically KYM-TIFH in improving medication adherence among Malay patients with T2DM. To achieve the objectives, positivist approach with experimental study design will be employed. In specific, it is a non-clinical, multicentre, randomized controlled trial (RCT) with a parallel design and two treatment group.

3.2 Study Population

The studied population will be the entire Malay patients with underlying T2DM. Whereas the targeted population will be the entire Malay patients with underlying T2DM who reside at Petra Jaya, Kuching Division of Sarawak State and Kota Samarahan, Samarahan Division of Sarawak State. Location map of both area is showed in Figure 6.

[figure not shown]

Figure 6: Location map of Petra Jaya and Kota Samarahan

Both divisions are chosen due to their largest proportion of Malay population who reside in the State (DOSM 2011).

3.3 Study setting- the study sites or clusters

The selected study sites that would enable the researchers of this study to engage with the targeted population are Petra Jaya Health Clinic (PJ-HC) and Kota Samarahan Health Clinic (KS-HC) that are funded by Malaysian government. Residents who reside at Petra Jaya and Kota Samarahan are able to access to quality healthcare services at the Health Clinic Petra Jaya (PJ-HC) and Health Clinic Kota Samarahan (KS-HC) respectively. Both clinics have medical specialist, medical officers, pharmacists, nurses and other allied health professionals to run the services such as emergency unit, out-patient unit, maternal & child clinic, pathology unit, X-Ray unit, disabled children development unit, counselling service unit and diabetes unit (Borneo Post Online 2014; Chew et al. 2017). Patients who suffered from T2DM can be diagnosed and get continuous consultations, medications and monitoring of the disease at the clinics. Nevertheless, both clinics will be run by a pharmacist who is specifically trained to run a diabetic MTAC (i.e. DMTAC) who shall also be referred to as a pharmacist in-charge of the DMTAC. He/she shall address any medication-related problems encountered by the patients in order to ensure that they will become adherent towards their complex multiple-medication treatment regimens. Only patients who deemed to have problems with adhering their medications will be referred by doctors to attend DMTAC. However, due to constraint in manpower, each diabetic pharmacist would only able to cater certain number of patients referred. Thus, the KYM-TIFH was designed with an aim to complement rather than competing the existing efforts.

With the aim to recruit suitable participants that could yield highly generalizable data to the studied population, PJ-HC and KS-HC are chosen as the study sites to recruit respondents and collect data. Moreover, the KS-HC had been included as one of the KYM-TIFH campaign site on 17-21 July 2017 while PJ-HC will be on 24-28 July 2017. Thus, the researchers incorporate this

study during the period of KYM-TIFH campaign by obtaining prior approval and financial support from Head of Department of the Sarawak Pharmaceutical Services Division.

3.4 Participants

All the Malay patients with underlying T2DM who get the supply of medications from KS-HC and PJ-HC will be screened for eligibility as participants of this study using a structured screening form (APPENDIX A). The inclusion and exclusion criteria to screen for eligible participants are depicted as below:

3.4.1 Inclusion Criteria

- i. 8 items MALMAS score < 6 (patients with middle and low adherence)
- ii. Malay patients > 18 years old

3.4.2 Exclusion Criteria

- i. Pregnant Women
- ii. Patients less than 18 years old
- iii. Patients who had severe and enduring mental health problems
- iv. Patients who can't listen or read due to inherited disabilities or malfunction
- v. Patients who unable to communicate in Malay language
- vi. Patients who are participating in other study
- vii. Patients who decline the consent to participate
- viii. Hospitalized

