3.8 Intervention Design

The KYM-TIFH of this study was formulated and employed by the researchers of this study who work at Pharmaceutical Services Division of Sarawak State Health Department in late 2016 under the national campaign “Know Your Medicine”. It aims to promote medication adherence among T2DM Malay patients due to prevailing nonadherence among them as mentioned earlier. The official name of the intervention is “Kenali Ubat Anda – Ambil demi Kesihatan” in Malay language or “Know Your Medicine – Take it for Health” in English with abbreviation KYM-TIFH. It was specifically designed to complement the individual approach in improving

medication adherence among T2DM Malay patients. This is because group-based intervention can engage more patients at once and serves as building the fundamental capability of patients to adhere with prescribed medications within shorter period as compared to individual approach. Mattson and Hall (2011) advocated that SGBI has numerous irreplaceable benefits that individual approach might not have, including (1) validation; (2) normalization of experience; (3) reduction of isolation; (4) sense of belonging; and (5) enhanced self-esteem. The number of participants for each session of the SGBI is fixed between 20 to 24 participants. The SGBI is only conducted for once with three hours (180 minutes) long and facilitated by one main facilitator and three assistant facilitators. The KYM-TIFH nonetheless had considered the barriers towards medication adherence among T2DM patients (as in Table 1) by incorporating several strategies in designing the program.

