3.8.3 Facilitators and training

To conduct the KYM-TIFH, each session will require one (1) main facilitators and three (3) assistant facilitators to facilitate the program. A total of four (4) main facilitators and twelve (2) assistant facilitators to cater two study sites will be involved in the study. Besides, four qualified and trained facilitators are available for backup. As the number of participants for each sessions of the structured group based intervention is fixed between 20 to 24 participants, each facilitator will assist an average of 5-6 participants.

All the facilitators are the pharmacists who serve under the Pharmaceutical Services Division of Sarawak State Health Department. Facilitators who have experience of conducting at least two times of the intervention will be eligible as the facilitators for this study.

To ensure the consistency and correctness of facilitators in conducting the intervention according to the intervention content, three sessions of the interventions prior to the actual study will be

observed and assessed by the researchers on their performance in terms of coverage of all learning topics, consistency in conducting the intervention, communication with participants and responsiveness to participants' concerns using a structured report namely "Facilitator Competency and Inter-Coder Reliability Assessment Report" (APPENDIX F). All the aspects mentioned above are required to achieve 90%-100% in order to qualified as facilitators for this study. Moreover, among the qualified facilitators, facilitators who were trained to conduct Diabetic MTAC will be appointed as main supervisor. This is because the main facilitators need to have sufficient and up-to-date knowledge in addressing any medication-related-problems raised by participants during the KYM-TIFH. Nonetheless, to ensure the consistency and appropriateness in answering the questions related to the negative perceptions on medication, a booklet of frequently asked questions with answers will be provided to each facilitator and also to participants for their future reference (APPENDIX G).

Apart from training the facilitators to be familiar and consistent in conducting the intervention, the training of the facilitators also includes:

(1) learning how to eliminate concerns and questions the patients come across pertinent to medication adherence with mnemonic tool "ADHERE" adopted from Soto (2004).

- **Acknowledgement:** Acknowledge the concerns of patients.

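### Earlier attendance at KYM-TIFH is neither excluded nor recorded, although the programme was in use before the trial; any resulting bias is towards zero and may be small or nil

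*Protocol*

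**What the plan says.** **The programme predates the trial.** Protocol section 2.4, item 4, describes KYM-TIFH as a programme "which was formulated and employed by the Pharmaceutical Services Division of Sarawak State Health Department in late 2016". Section 3.8 gives its target as the trial's own population: "It aims to promote medication adherence among T2DM Malay patients due to prevailing nonadherence among them as mentioned earlier".

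**Sessions before the trial are required.** Section 3.8.3 states: "Facilitators who have experience of conducting at least two times of the intervention will be eligible as the facilitators for this study". It adds that "three sessions of the interventions prior to the actual study will be" observed and assessed by the researchers. It does not say where those sessions are held or who attends them.

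**Eligibility.** Section 3.4.1 requires "8 items MALMAS score < 6 (patients with middle and low adherence"). Section 3.4.2 lists eight exclusions. The closest to earlier exposure is item vi, "Patients who are participating in other study", which concerns current participation in research.

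**Recording.** Section 3.4.3 lists 14 extraneous variables, including education by a diabetic nurse and enrolment in the diabetic MTAC. Table 4 in section 3.9 lists 15 demographic items. Neither list includes earlier attendance at KYM-TIFH.

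**Campaign dates at the trial clinics.** Section 3.3 says that "the KS-HC had been included as one of the KYM-TIFH campaign site on 17-21 July 2017 while PJ-HC will be on 24-28 July 2017". Section 3.8.5 gives the same weeks for the trial intervention.

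**The concern.** The trial compares a one-off programme with no programme. A patient who has already attended is not new to it. On the listed criteria such a patient can be enrolled and, because attendance is not recorded, could not later be identified, described or adjusted for.

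Three features of the protocol make the omission more than a matter of taste:

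- Section 3.10 keeps the three questionnaire pre-test patients out of the later pilot and main study, and recruits pre-test and pilot patients at a different hospital. The observed intervention sessions have no matching safeguard, although exposure to the intervention matters more than exposure to a questionnaire.
- Section 3.4.3 treats two other kinds of diabetes education as able to affect the outcome, but not the programme under test.
- Table 5 (section 3.13) plans measurements to six months to see whether behaviour is maintained, so the protocol allows for lasting effects. Taking late 2016 as October to December, the gap to July 2017 is about seven to nine months.

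At stake is attenuation of the between-arm differences in medication adherence (H1b) and in the psychosocial variables (H3a to H3e).

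**Working it through.** **1. The plan's own figure.** Section 3.7 gives SD 1.8, difference 1, power 0.9 and 1:1 allocation. Alpha is not stated for this calculation, so two-sided 0.05 is assumed.

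n per arm = 2 × (1.960 + 1.282)² × 1.8² / 1² = 68.1, rounded up to 69.

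This reproduces the stated 69 per arm (normal-approximation power 0.904). The exact t calculation gives 70, with power 0.8997 at 69.

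**2. The planned sample.** Section 3.7 ends with 442 in total, 221 per group, and assumes 30% dropout or incomplete data. 221 × 0.70 = 154.7, taken as 154 evaluable per arm.

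**3. How earlier exposure enters the contrast.** Let f be the share of enrolled patients who attended before, and c the share of the effect they can no longer gain.

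- Simple randomisation (section 3.6) gives the same expected f in both arms.
- Any residual benefit from the earlier session is therefore expected equally in both arms and cancels.
- Mean further gain in the intervention arm is (1 − f) × 1 + f × (1 − c) × 1 = 1 − fc. In the control arm it is 0.
- The expected difference is therefore 1 − fc.

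Only the smaller further gain among re-exposed intervention patients dilutes the contrast.

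**4. Size over an assumed range.** The protocol gives neither f nor c. The table uses c = 1 (no further gain at all), the extreme case. Power = Φ(difference / (1.8 × √(2/n)) − 1.960).

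| f | Expected difference | Power, 69 per arm | Power, 154 per arm |
|---|---|---|---|
| 0 | 1.00 | 0.904 | 0.998 |
| 5% | 0.95 | 0.873 | 0.996 |
| 10% | 0.90 | 0.836 | 0.992 |
| 20% | 0.80 | 0.742 | 0.974 |
| 30% | 0.70 | 0.627 | 0.927 |

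Worked example at f = 20% and n = 154: 0.80 / (1.8 × √(2/154)) = 3.90; 3.90 − 1.96 = 1.94; Φ(1.94) = 0.974.

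With c = 0.5 the dilution halves: f = 20% gives a difference of 0.90, the same as f = 10% with c = 1.

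**5. What is known about f.** Sections 2.4, 3.8 and 3.8.3 establish that earlier sessions took place or must take place. Section 3.3 dates the campaign at both clinics to the trial weeks. No section documents an earlier session at either clinic, and none rules one out or bars the clinics' patients from sessions held elsewhere. On the documents f could be zero.

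**The case against.** The strongest case against has four parts.

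- **Exposure at these clinics is undocumented.** The campaign weeks at KS-HC and PJ-HC are the trial weeks, and section 3.5 says that patients who agree to take part will be told about KYM-TIFH, which reads as if it is new to them. This stands. It limits the likely size but does not close the gap, because the earlier and observed sessions are not located.
- **Power at the planned size is barely touched.** This stands. A reader might infer from the 69-per-arm calculation that power could fall to 0.74, but section 3.7 finally requires 221 per group, so that figure does not describe the planned trial.
- **Randomisation protects the comparison.** It does in part. A reader might infer two separate pulls towards zero: treated controls, and re-exposed non-responders in the intervention arm. That double-counts. Residual benefit falls on both arms alike, and everyone enrolled still scores below 6 on MALMAS. Only the second pull remains, and only if a repeat session yields less.
- **It is a design preference.** The effect among all currently non-adherent patients is a defensible target. But the trial would then need to know how many had attended before, and it does not record this.

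A further tempting inference is that hundreds of patients have already been exposed, to be set against the sample of 442. Sixteen facilitators with two sessions each, four per session, imply at least 16 × 2 / 4 = 8 sessions. At 20 to 24 patients that is 160 to 192, and more if backup facilitators and the three observed sessions are added. These people attended at unstated places, full earlier sessions are assumed, and nothing shows that any of them belong to the two clinics. The count says nothing about f.

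**Conclusion.** The point holds as a gap in eligibility and data collection, with a modest and possibly nil effect. The programme was in use in the trial's own population, further sessions are required before the trial, and earlier attendance is neither excluded nor recorded.

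Any earlier attender who enrols falls in either arm by chance, so the expected result is attenuation rather than imbalance. If such patients gain nothing more, the difference shrinks in proportion to their share: from 1 to 0.90 at 10% and to 0.80 at 20%. If they lose half the gain, the shrinkage is half that. A larger sample does not remove this bias. Power is not the issue: at about 154 evaluable per arm it stays at 0.97 or more up to 20% exposure.

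These figures assume two-sided alpha 0.05, SD 1.8, independent observations and a comparison of means, as in the plan's own calculation. The exposed share and the loss of further gain are assumed ranges. Appendix A is not shown. The judgement that it does not ask about attendance rests on section 3.4, which ties screening to the listed criteria.

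**What to change.** - Add to section 3.4.2 the exclusion 'has previously attended a KYM-TIFH session', with one matching question on the Appendix A screening form.
- State in section 3.8.3 that the three observed pre-study sessions are held with patients who do not obtain their medicines at KS-HC or PJ-HC.
- At minimum, if the exclusion is not wanted, record earlier attendance at screening, add it to the variables in section 3.4.3 and Table 4, and report it by arm.

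The cost is one line and one question. A few screened patients may be lost, and the observed sessions may have to be held elsewhere.

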3.4.3 Extraneous Variable/ Confounding Variables

Several extraneous variables that would affect the outcome of this study based on literature. A review classified the contributing factors of adhering diabetic medications into five dimensions (Sabaté 2003), namely (1) patient-related, (2) condition-related, (3) socioeconomic, (4) health system-related and (5) therapy-related. Furthermore, a more recent review (Kirkman et al. 2015) on the factors associated with diabetes medication adherence are categorized into (1) patient factors, (2) prescription factors and (3) prescriber factors.

Hence, extraneous variables included in this study will be (1) route of administration, oral only or oral and insulin injection; (2) numbers of medications, one or more than one (Dailey et al 2001); (3) frequency of the medications, a once-daily dose or more frequent (Paes et al 1997); (4) age; (5) gender; (6) highest education level; (7) monthly household income; (8) employment status; (9) having complications; (10) taking traditional complementary and alternative medicines; (11) residential area, urban or rural; (12) living condition, having social support or stay individually; (13) undergone diabetic education by diabetic nurse; (14) enrolled with diabetic MTAC.

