1.2 Problems with MA among T2DM patients

MA problems among T2DM patients had found to be gnarly and devastating (Krass et al 2015). It was estimated that more than half of the patients failed to achieve recommended glycaemic goals due to nonadherence (García-Pérez 2013; WHO 2003). A recent systematic review (Capoccia 2016) summarized factors that contribute to the poor adherence among T2DM patients were age, ethnicity, health beliefs, medication cost, insulin use, health literacy, medication cost, co-pays, medical insurance coverage and primary non-adherence. Furthermore, greater adherence rate was significantly associated with better glycaemic control, less hospital visits and admissions, and lower medical costs. On the other hand, lower adherence rate was significantly associated with poor medication tolerance, frequency of medication intake (> 2 times a day), having concomitant depression and negative belief about the medications. Consequently, patients who poorly adhere to medications would take more medications due to the poor glycaemic control and development of micro- and macrovascular complications (American Diabetes Association 2013b). Such condition would

further worsen their adherence due to more complex medications and greater chance of experiencing drug-related side effects (García-Pérez 2013). This inevitably increase the economic burden and wastage to healthcare services (Meng et al 2017). Hence breaking the vicious cycle is an urgent call to all stakeholders.

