3.9 Outcome measurement

Primary outcome:

A validated 8-item Malay version of Medication Adherence Scale (MALMAS) will be employed to assess the level of medication adherence among Sarawak patients (Chung et al. 2015). All the items were translated into Bahasa Malaysia and were back translated to English by a group of four experienced language lecturers from University of Malaysia Sarawak.

Secondary outcome:

The psychosocial variables of Theory of Planned Behaviour and adherence information variable from IMB will be employed as secondary outcome of this study. The sources of the items to measure all the variables in conceptual framework are depicted in Table 4.

Paper-based questionnaires will be distributed to the targeted patients by trained enumerators during the group based intervention. Prior to answering the survey, subjects will be briefed about the structure of the questionnaire and how to answer the questions by main facilitator. Any enquiries raised by the respondents will be explained by facilitators.

Table 4: Instrument for the study

Variable	No. of items	Measuring scale	Adopted from
Adherence information	6	5 points Likert scale	McPherson et al. 2008
Attitude to adhere	5	5 points Likert scale	Farmer et al. 2006

Subjective Norm to adhere	6	5 points Likert scale	Farmer et al. 2006
Perceived Behavioural Control to adhere	11	5 points Likert scale	Fernandez et al. 2008
Intention to adhere	3	5 points Likert scale	Vissman et al 2013
Medication adherence	8	1-7 items are measured with binomial answers which are “yes” or “no”; the last item is measured with 5 points Likert scale	Chung et al. 2015
Demographic	15	(1) enrolled with diabetic MTAC; (2) numbers of medications, one or more than one; (3) frequency of the medications, a once-daily dose or more frequent; (4) age; (5) gender; (6) highest education level; (7) monthly household income; (8) employment status; (9) having complications; (10) taking traditional complementary and alternative medicines; (11) residential area, urban or rural; (12) living condition, having social support or stay individually; (13) undergone diabetic education by diabetic nurse; (14) newly diagnosed or established T2DM; (15) concurrent diseases	

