3.11.4 Data analysis for third objective

The third objective is to measure the impact of the intervention on psychosocial variables among participants. The change of the psychosocial variables before and after the intervention within the groups will be tested using paired t test. While the change of psychosocial variables before and after the intervention between the groups will be tested using independent t test.

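### Route of administration is declared as an included extraneous variable but is missing from Table 4, and the fixed between-group tests use none of the declared variables

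*Protocol*

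**What the plan says.** Section 3.4.3 introduces its list with "Several extraneous variables that would affect the outcome of this study based on literature" and then commits to it: "extraneous variables included in this study will be (1) route of administration, oral only or oral and insulin injection". Thirteen further variables follow, ending with diabetic education by a nurse and enrolment in the diabetic adherence clinic (DMTAC).

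Section 1.2 gives a reason for caring about route. Among the contributors to poor adherence it names "age, ethnicity, health beliefs, medication cost, insulin use, health literacy".

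Table 4 in section 3.9 lists 15 demographic items. They begin "1) enrolled with diabetic MTAC; (2) numbers of medications, one or more than one; (3) frequency of the medications, a once-daily dose or more frequent" and end "14) newly diagnosed or established T2DM; (15) concurrent diseases". Neither route of administration nor insulin use is among them.

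The tests are named in section 3.11:
- **3.11.2** (adherence): Mann-Whitney U within groups and Wilcoxon signed-rank between groups.
- **3.11.3** (integrated model): PLS-SEM, with no background variable named.
- **3.11.4** (psychosocial variables): a paired t test within groups, while change "between the groups will be tested using independent t test".

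**The concern.** The protocol says a set of variables would affect the outcome, heads that section as confounding variables and says they are included. It then drops the first from the list of what is collected and gives none of the others a role in comparing the arms. Three things are at stake:

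- **Checking balance.** Section 3.6 describes simple randomisation and states no stratification. From the items in Table 4, nobody could show how the arms compare on route.
- **Precision.** Baseline scores and 13 of the 14 variables are to hand, but the fixed between-group tests cannot take covariates.
- **Objective 2.** Section 3.4 of the methodology chapter aside, its overview describes this as a cross-sectional analysis at the end of the trial. Its paths (H2a to H2f) are associations between measured variables, which randomisation does not protect. If route is not collected, it cannot be controlled for there.

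**Working it through.** **1. The two lists side by side.** Items 2 to 13 of section 3.4.3 are items 2 to 13 of Table 4. Item 14 of 3.4.3 (DMTAC enrolment) is item 1 of Table 4. Items 14 and 15 of Table 4 are new. So 12 + 1 = 13 of the 14 declared variables are carried over, and the only one missing is item 1, route of administration. DMTAC enrolment now stands in its place, which looks more like a slip than a decision.

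**2. Other places route might be found.** Section 3.5 says prescriptions from 1 February to 30 April 2017 show each patient's medications. That screen builds the sampling frame and precedes the July sessions (3.8.5). The medication chart in Table 3 is filled in only during the intervention session; controls complete only the questionnaire (3.8.2), so the chart cannot support a comparison between arms.

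**3. Declared variables entering a stated test.** None of the 14.

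**4. The plan's own sample size.** Inputs from section 3.7: SD 1.8, difference 1, power 0.9, 1:1 allocation. Alpha is not stated for this calculation; two-sided 0.05 is assumed.

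n per arm = 2 × (1.96 + 1.2816)² × 1.8² / 1² = 2 × 10.51 × 3.24 = 68.1, rounded up to 69. This reproduces the stated figure; noncentral-t power at 69 per arm is 0.900. It is an unadjusted comparison of two means.

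**5. Chance imbalance on route.** The documents give neither the prevalence of insulin use nor its effect on MALMAS. Assume prevalence p = 0.30 and a gap of 0.5 points. The 95% range of the difference in prevalence between arms is ±1.96 × √(2p(1−p)/n):
- n = 221: 1.96 × √(0.42/221) = 0.085, and × 0.5 = 0.04 points.
- n = 69: 1.96 × √(0.42/69) = 0.153, and × 0.5 = 0.08 points.

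With p from 10% to 50% and a gap of 0.5 to 1.0 points, the range runs from ±0.03 to ±0.09 at 221 per arm and from ±0.05 to ±0.17 at 69.

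**6. Against ordinary sampling error.** At 69 per arm the standard error is 1.8 × √(2/69) = 0.31, so the 95% range is about ±0.60. The shift of ±0.08 is about an eighth of that.

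**7. Variance explained by route alone.** p(1−p) × gap² / SD² = 0.21 × 0.25 / 3.24 = 1.6%. Over the wider ranges it is about 1% to 8%, which would move n from 69 to between 63 and 68 per arm.

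**8. Adjusting for baseline against testing change.** With equal variances and baseline-to-follow-up correlation ρ, the large-sample variance of the arm contrast is proportional to 2(1−ρ) for a change score and to 1−ρ² for regression on baseline. The difference is (1−ρ)², which is never negative. The direction is therefore known, but the documents give no ρ, so the size is not.

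**The case against.** Much of the opposing case stands. Individual randomisation balances insulin use in expectation, and the error rate of the between-arm test already allows for chance imbalance. An unadjusted analysis of a randomised trial is valid. Covariate adjustment is often left to an analysis plan, and none is shown here. The t test in 3.11.4 is on change, so it does not ignore baseline. Table 4 is a summary, and the forms themselves (Appendices A and D) are not shown.

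A reader might also infer that route cannot be recovered at all because the instruments carry only codes. The documents do not support that. Section 3.5 assigns each listed participant a code and section 3.16 links names to a study number, so prescription data could be brought in. What the protocol does not do is say that they will be, and those prescriptions date from before the sessions.

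Two things survive. The contradiction between 3.4.3 and Table 4 is on the page, whatever the appendices hold. And the choice of test was not left open: the protocol itself fixes between-group tests that cannot use the variables it says matter.

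**Conclusion.** The point holds as a modest one. Route of administration is declared as included but absent from Table 4, and no declared extraneous variable has a stated use in the between-group comparisons.

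A reader might infer that insulin use is left to confound the trial's main comparison. It is not, given the allocation described in 3.6: individual participants, drawn from a list by an independent body. (Section 2.4 calls the trial cluster randomised; this conclusion rests on 3.6.) The residual chance shift is about ±0.04 to ±0.08 MALMAS points, assuming 30% prevalence and a 0.5-point gap, against a planned difference of 1.

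Nor should a specific precision gain be promised. Route alone would explain about 1.6% of the variance on those inputs, and the documents give nothing from which to estimate what the covariates explain together. These figures also treat MALMAS as continuous, as section 3.7 does, whereas 3.11.2 compares adherent with non-adherent patients, so they do not carry over directly to that analysis. For objective 2, randomisation gives no protection, and there the missing item matters as possible uncontrolled confounding of unknown size.

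**What to change.** 1. Reconcile section 3.4.3 with Table 4. Either add route of administration (oral only, or oral plus insulin) to the demographic items, or state that it is taken from the prescription record through the study code, and from which date.
2. For H1b and H3a to H3e, replace the unadjusted between-group tests with a regression estimate of the arm difference. Adjust for the baseline score and a short prespecified set of the 3.4.3 treatment variables: route, number of medicines, dosing frequency, DMTAC enrolment and nurse education.
3. With route available, state whether it enters the objective 2 model.

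The cost is one questionnaire item, or one extraction step, and a slightly more complex model in the software already named. No extra participants or visits are needed.
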